2. LIST OF ABBREVIATIONS

See Medicine Glossary:

<http://glossary>

Term	Definition / description
ALT	Alanine Aminotransferase
ANCOVA	Analysis of Covariance
AST	Aspartate Aminotransferase
AUC _{0-tz}	Area under the concentration-time curve of the analyte in serum over the time interval from 0 to the last quantifiable drug concentration
AUC _{0-∞}	Area under the concentration-time curve of the analyte in plasma over the time interval from 0 extrapolated to infinity
BLQ	Below limit of quantification
BMI	Body mass index
CI	Confidence Interval
C _{max}	Maximum measured concentration of the analyte in plasma
CSD	Company standard displays
CV	Arithmetic Coefficient of Variation
DBLM	Database Lock Meeting
DILI	Drug induced liver injury
gCV	Geometric Coefficient of Variation
gMean	Geometric Mean
LLOQ	Lower limit of quantification
LLT	Lower Level Term
IQRMP	Integrated Quality and Risk Management Plan
Max	Maximum
Min	Minimum
N	Number non-missing observations
P10	10 th percentile
P90	90 th percentile
PKS	PK parameter analysis set
Q1	1 st quartile
Q3	3 rd quartile
RAGe	Report Appendix Generator system

Term	Definition / description
RCTC	Rheumatology Common Toxicity Criteria
REP	Residual Effect Period
SD	Standard Deviation
t_{max}	Time from dosing to maximum measured concentration of the analyte in plasma
TS	Treated Set
UDAEC	User Defined Adverse Events Concepts
ULN	Upper Limit of Normal
WHO-DD	World Health Organization Drug Dictionary

3. INTRODUCTION

As per ICH E9 ([1](#)), the purpose of this document is to provide a more technical and detailed elaboration of the principal features of the analysis described in the protocol, and to include detailed procedures for executing the statistical analysis of the primary and secondary variables and other data.

This trial statistical analysis plan (TSAP) assumes familiarity with the Clinical Trial Protocol (CTP), including Protocol Amendments. In particular, the TSAP is based on the planned analysis specification as written in CTP Section 7 “Statistical Methods and Determination of Sample Size”. Therefore, TSAP readers may consult the CTP for more background information on the study, e.g., on study objectives, study design and population, treatments, definition of measurements and variables, planning of sample size, randomisation.

Study data (including data entered in the RAVE EDC system and external data provided by suppliers) will be stored in a Clinical Data Repository (CDR).

Pharmacokinetic (PK) parameters will be calculated using Phoenix WinNonlinTM software (version 6.3 or higher, [REDACTED]).

The statistical analyses will be performed within the validated working environment CARE, including SAS[®] (current Version 9.4, by [REDACTED]), and a number of SAS[®]-based tools (e.g., macros for the analyses of AE data or laboratory data; Report Appendix Generator system (RAGe) for compilation/formatting of the CTR appendices).

4. CHANGES IN THE PLANNED ANALYSIS OF THE STUDY

All analyses as planned in the CTP will be performed and are described in more detail in this TSAP. The following changes compared to the protocol will be made:

In CTP section 7.3 the following was defined: *Important protocol deviation (IPD) categories will be specified in the Integrated Quality and Risk Management (IQRM) Plan. IPDs will be identified no later than in the Report Planning Meeting, and the IPD categories will be updated as needed.* Due to SOP changes, the IPD categories are no longer available in IQRM plan but included in an Excel spreadsheet (3). The IPD categories originally defined in IQRM plan were transferred to the IPD specification file. Minor changes regarding the IPD categories were performed only.

In CTP section 5.2.6.1.4 the following definition was used for an AE of special interest: *Severe infections (according to RCTC grading in ISF).* As it is a healthy volunteer study, no RCTC grades were applied, therefore the definition ‘Severe infections (according to AE intensity grades as ticked in eCRF)’ was used for analysis.

In CTP section 7.3, the following definition was included by mistake:

Plasma concentrations and/or parameters of a subject will be considered as non-evaluable, if for example

- *The subject experienced emesis that occurred at or before two times median t_{max} of the respective treatment (Median t_{max} is to be determined excluding the subjects experiencing emesis),*

As route of study drug administration is sc or iv, emesis has no effect on PK evaluability and will not be considered for PK analysis.

5. ENDPOINTS

5.1 PRIMARY ENDPOINTS

The primary objective of this trial is to investigate PK, including dose proportionality, following single IV and SC doses of Spesolimab in healthy Chinese subjects. Primary endpoints are $AUC_{0-\infty}$ and C_{max} of Spesolimab.

5.2 SECONDARY ENDPOINTS

5.2.1 Key secondary endpoint

This section is not applicable as no key secondary endpoints have been defined in the CTP.

5.2.2 Secondary endpoints

Section 2.1.3 of the CTP:

The occurrence of treatment-emergent AEs (e.g. number of subjects with treatment-emergent AEs).

The occurrence of drug-related AEs (e.g. number of subjects with drug-related AEs).

Safety and tolerability of Spesolimab will be assessed based on:

- *Safety laboratory parameters*
- *12-lead ECG*
- *Vital signs (blood pressure [BP], pulse rate [PR], respiratory rate [RR], body temperature)*
- *Immunogenicity (ADA)*

5.4 OTHER VARIABLES

There are the following other parameters which will be listed and tabulated:

Subject information:

- Informed consent
- Relevant medical history
- Concomitant therapy
- Inclusion/Exclusion criteria

Demographic data:

- Gender
- Height
- Weight
- Smoking history
- Alcohol history
- Race
- Ethnicity

Age [years] will be determined as the difference between year of informed consent and year of birth.

BMI will be calculated as weight [kg] / (0.01 * height [cm])².

6. GENERAL ANALYSIS DEFINITIONS

6.1 TREATMENTS

For basic study information on investigational products, assignment of treatment sequences and selection of doses, please see CTP, Sections 3 and 4.

The study will be performed as a single dose, open-label non-randomized study in parallel-group design.

It is planned to include up to 60 healthy male and female subjects in the trial. The subjects will be assigned to 5 groups each consisting of 10 subjects with at least 3 subjects for each gender within each dose group. The cohorts within each SC and IV dose groups will be dosed sequentially.

For details of dosage and formulation see Table 6.1:1 below.

Table 6.1: 1 Labels for treatments for use in the CTR

Dose group	Treatment	Short label
1	A BI 655130, 450 mg, iv, once	Speso 450mg iv
2	B BI 655130, 900 mg, iv, once	Speso 900mg iv
3	C BI 655130, 1200 mg, iv, once	Speso 1200mg iv
4	D BI 655130, 300mg, sc, once	Speso 300mg sc
5	E BI 655130, 600mg, sc, once	Speso 600mg sc

The following separate study phases will be defined for the analyses of AEs:

- **Screening** (ranging from 0:00h (midnight) on day of informed consent until first administration time of study drug Spesolimab))
- **On treatment**
 - **BI treatment** (separately for each treatment, ranging from the time of first administration of Spesolimab / start of infusion of Spesolimab until time of administration + REP (defined as 16 weeks) / end of infusion + REP (defined as 16 weeks))
 - **Follow-up (F/U)** (ranging from administration / end of infusion of Spesolimab + REP until 0:00h (midnight) on the day after trial completion date))

The following AE displays will be provided in the report:

Section 15.3 and Appendix 16.1.13.1.8 (for ClinicalTrials.gov) of the CTR displays:

In these displays, the on treatment phase will be analysed (labelled with the name of the study treatment (short label)). Screening and Follow-up phases will not be included in this analysis.

The following totals will be provided in addition:

- a total over all on treatment phases included in this analysis ("Total") (Appendix 16.1.13.1.8 only)
- a total over all on treatment phases included in this analysis ("Total iv") (tables including iv treatment groups)
- a total over all on treatment phases included in this analysis ("Total sc") (tables including sc treatment groups)

Tables for ClinicalTrials.gov will be provided including both sc and iv groups.

In Section 15.4 and Appendix 16.2 (Listings) of the CTR displays, the screening and follow-up period will be included and no totals will be provided.

Tables of vital signs and laboratory values will present results for the above mentioned on treatment phase.

For detailed information on the handling of the treatments refer to Technical TSAP ADS (analysis data set) plan and Analysis Data Reviewers guide.

6.2 **IMPORTANT PROTOCOL DEVIATIONS**

Data discrepancies and deviations from the CTP will be identified for all treated subjects.

Consistency check listings (for identification of deviations of time windows) and a list of protocol deviations (e.g. deviations in drug administration, in blood sampling times, etc.) will be provided to be discussed at the Report Planning Meeting and database lock meeting (RPM/DBLM). At this meeting, all manual deviations identified at the sites by the CRAs and deviations too complex to program will be reviewed by the trial team to decide which are considered important. For definition of important protocol deviations (iPD), and for the process of identification of these, refer to the Boehringer Ingelheim (BI) SOP "Identify and Manage Important Protocol Deviations (iPD)" (2).

If any iPDs are identified, they are to be summarised into categories and will be captured in the RPM/DBLM minutes via an accompanying Excel spreadsheet.

Categories which are considered to be iPDs in this trial were defined in the integrated quality and risk management plan (IQRMP) prior to trial initiation. The IPD list was transferred into the IPD specification file (due to changes in the SOP) (3). Within this transfer some minor adaptations were done to comply with new naming conventions and categorisations. IPDs will be identified no later than in the Report Planning Meeting and the IPD categories will be updated as needed. The decision on exclusion of subjects from analysis sets will be made after discussion of exceptional cases and implications for analyses.

The iPDs will be summarised and listed.

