7.3.4 Safety analyses

Safety will be assessed for the endpoints listed in [section 2.1.2](#) and 2.2.2 based on the TS. Safety analyses will be descriptive in nature and will be based on BI standards. No hypothesis testing is planned. Treatments will be compared in a descriptive way. Tabulations of frequencies/proportions will be used for the evaluation of categorical (qualitative) data, and tabulations of descriptive statistics will be used to analyse continuous (quantitative) data.

Measurements (such as vital signs, or laboratory parameters) or AEs will be assigned to treatments (see [section 4.1](#)) based on the concept of treatment emergent AEs. Therefore,

Proprietary confidential information © 2021 Boehringer Ingelheim International GmbH or one or more of its affiliated companies

measurements planned or AEs recorded prior to intake of trial medication will be assigned to 'screening', those between trial medication intake and end of REP will be assigned to the treatment period. Events occurring after the REP but prior to trial termination date will be assigned to 'follow-up'. These assignments including the corresponding time intervals will be defined in detail in the TSAP. Note that AEs occurring after the last per protocol contact but entered before database lock will be reported to Pharmacovigilance only and will not be captured in the trial database.

Additionally, further treatment intervals (called analysing treatments) may be defined in the TSAP in order to provide summary statistics for other than above periods, such as combined treatments, on-treatment totals or periods without treatment effects (such as screening and post-trial intervals).

AEs will be coded using the Medical Dictionary for Regulatory Activities (MedDRA). Frequency, intensity and causal relationship of AEs will be tabulated by treatment, primary system organ class and preferred term. SAEs, AESIs (see [section 5.2.6.1.4](#)) and other significant AEs (according to ICH E3) will be listed separately.

Laboratory data will be compared to their reference ranges. Values outside the reference range will be highlighted in the listings. Additionally, differences from baseline will be evaluated.

Vital signs or other safety-relevant data observed at screening, baseline, during the course of the trial and at the end-of-trial examination will be assessed with regard to possible changes compared to findings before start of treatment.

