7.8.1 Adverse Events

AEs will be coded with the most recent version of MedDRA.

The analyses of AEs will be descriptive in nature and will be based on BI standards as presented in “Analysis and Presentation of Adverse Event Data from Clinical Trials – Display Template” [BI-KMED-BDS-HTG-0041] ([8](#)).

The standard AE analyses will be based on the number of subjects with AEs (and not on the number of AEs).

The analysis of AEs will be based on the concept of treatment emergent AEs. That means that all AEs will be assigned to 'screening', 'on treatment' or 'follow-up' phases as defined in [Section 6.1](#). AEs will be analysed based on actual treatments, as defined in [Table 6.1: 1](#).

Section 1.2.6 of the CTP: The residual effect period (REP) of Spesolimab is 16 weeks.

According to the clinical study protocol, adverse events of special interest (AESI) will be analysed:

Section 5.2.6.1.4 of the CTP: The following are considered as AESIs in this trial:

- *Hepatic injury, as defined by the following alterations of hepatic laboratory parameters:*
 - *an elevation of AST (Aspartate Aminotransferase) and/or ALT (Alanine Aminotransferase) ≥ 3 -fold ULN combined with an elevation of total bilirubin ≥ 2 -fold ULN measured in the same blood sample, or*
 - *ALT, and/or AST elevations ≥ 10 -fold ULN*

These lab findings constitute a hepatic injury alert and the subjects showing these lab abnormalities need to be followed up according to the 'DILI checklist' provided in the ISF. In case of clinical symptoms of hepatic injury (icterus, unexplained encephalopathy, unexplained coagulopathy, right upper quadrant abdominal pain, etc.) without lab results (ALT, AST, total bilirubin) available, the Investigator should make sure that these parameters are analysed, if necessary in an unscheduled blood test. Should the results meet the criteria of hepatic injury alert, the procedures described in the DILI checklist should be followed.

- *Systemic hypersensitivity including infusion reaction and anaphylactic reaction:*
Any suspicion of severe infusion reaction systemic/hypersensitivity reaction and of any potential cases of anaphylaxis should be defined and assessed using the criteria discussed in the statement paper from Sampson HA (Appendix 10.1.3, R11-4890).
- *Severe infections [...]*
- *Opportunistic and mycobacterium tuberculosis infections*

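### On the most natural reading of the SAP, the Day 176 end-of-trial labs and vital signs fall outside the by-visit tables and the eDISH plot; labelled follow-up rows would close the gap

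*SAP*

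**What the plan says.** **Phases.** SAP 6.1 runs treatment from dosing to 16 weeks (the residual effect period, REP) after administration or end of infusion. Follow-up then runs to trial completion. SAP 7.8.1 states that "all AEs will be assigned to 'screening', 'on treatment' or 'follow-up' phases".

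**Tables.** For labs and vital signs, SAP 6.1 says: "Tables of vital signs and laboratory values will present results for the above mentioned on treatment phase". For the adverse event (AE) displays in report Section 15.3 it says: "Screening and Follow-up phases will not be included in this analysis". For report Section 15.4 and Appendix 16.2 (the listings), "the screening and follow-up period will be included and no totals will be provided".

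**Detail by domain.**
- SAP 7.8.2 summarises lab values and on-treatment differences from baseline by visit, with last, minimum and maximum on treatment. It limits the eDISH plot to the on-treatment period.
- SAP 7.8.3 summarises blood pressure, pulse rate and respiratory rate over time, lists body temperature only, and shows the difference from baseline in the vital-sign listing.
- SAP 7.8.5 tabulates body weight, measured at screening and EoTrial, with change from baseline.

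**Protocol.** Both Flow Charts schedule safety labs and vital signs at Day 176 ±3. Protocol 7.3.4 applies its phase rule to measurements as well as AEs: "those between trial medication intake and end of REP will be assigned to the treatment period". The same section says that vital signs or other safety-relevant data "at the end-of-trial examination will be assessed with regard to possible changes compared to findings before start of treatment", and that "tabulations of descriptive statistics will be used to analyse continuous (quantitative) data".

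**The concern.** The closing safety examination is the one scheduled look at labs and vital signs after the REP, and all 50 planned subjects are due it. If the tables stop at Day 113, no by-visit lab or vital-sign table shows by dose group whether values have returned to, or moved away from, baseline at the end of observation.

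An ALT or bilirubin rise first seen at Day 176, for example, would be listed and flagged if out of range. It would be missing from the by-visit lab table, from the on-treatment maximum and from the eDISH plot. The SAP would then summarise end-of-trial body weight but not end-of-trial liver tests or blood pressure.

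What is at stake is the completeness of the safety summary. No data are lost, no PK endpoint is touched, and reporting of serious AEs and AEs of special interest to the sponsor is unaffected.

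**Working it through.** **1. Check the plan's day numbering.** Dosing is on Day 1, so study day = hours/24 + 1. The Flow Charts give 4200 h for EoTrial: 4200/24 + 1 = 176, as stated. The same formula gives Day 29 (672/24 + 1) and Day 92 (2184/24 + 1), also as stated.

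**2. End of the on-treatment phase.** The REP is 16 weeks (Protocol 1.2.6; SAP 6.1). 16 × 7 = 112 days after dosing, i.e. Day 113. For IV groups the clock starts at the end of a 90-minute infusion, which adds 1.5 h and changes nothing.

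**3. Where EoTrial falls.** 176 − 113 = 63 days (9 weeks) after the cut. With the ±3-day window the range is 60 to 66 days, so even an examination on Day 173 is in follow-up.

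**4. Scheduled post-dose assessments (both Flow Charts).**

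| Domain | Scheduled post-dose | On or before Day 113 | After Day 113 |
|---|---|---|---|
| Safety labs (days) | 4, 8, 22, 29, 92, 176 = 6 | 5 | 1 (Day 176) |
| Vital signs (time points) | 10 on Day 1; 2 on Day 2; 1 on Day 3; Days 8, 22, 29, 176 = 17 | 16 | 1 (Day 176) |

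The ten Day 1 points are 0:10, 0:30, 1:00, 1:30, 2:00, 3:00, 4:00, 6:00, 8:00 and 12:00. The two Day 2 points are 24:00 and 32:00.

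**5. Distance from the last tabulated set to EoTrial.** EoTrial is 175/7 = week 25. Day 29 is 28/7 = week 4 and Day 92 is 91/7 = week 13. The gap is 25 − 4 = 21 weeks for vital signs and 25 − 13 = 12 weeks for labs. Most of the vital-sign gap comes from the visit schedule, since none are scheduled between Day 29 and Day 176. The SAP restriction removes one time point.

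**6. Which reading of the SAP is the natural one.**
- For exclusion of Day 176: SAP 6.1 ends treatment at the REP, limits the lab and vital-sign tables to the on-treatment phase, and says the AE displays cover on treatment without follow-up. SAP 7.8.1 names three separate phases.
- Against: in SAP 6.1, Follow-up is printed as a sub-item under On treatment; those phases are introduced for the AE analyses; and SAP 7.8.3 says over time without giving an end day.

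The first set is explicit and the second is mostly layout and silence, so exclusion is the more natural reading, but it is not certain.

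**The case against.** **The cut is the protocol's own.** This stands. Protocol 7.3.4 assigns measurements as well as AEs to the treatment period up to the end of the REP and leaves the detailed intervals to the SAP. A reader might infer that SAP 4, which says all protocol analyses will be performed, conceals an undeclared change. The documents do not support that. Protocol 7.3.4 says end-of-trial findings will be assessed for change; it does not promise a Day 176 summary row.

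**Follow-up data may be summarised elsewhere.** A reader might infer that Day 176 data appear only in listings. That is not established. SAP 6.1 names report Section 15.4 as well as Appendix 16.2 for displays that include follow-up, and SAP 7 places safety analyses in Sections 15.1 to 15.4. The content of Section 15.4 is not specified, and the sponsor's laboratory display standard and technical SAP are not available here.

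**Change from baseline is partly covered already.** This also stands. Individual values are listed, and the vital-sign listing shows the difference. SAP 7.8.2 says lab differences to baseline will be calculated, without a phase limit in that sentence. Clinically relevant findings become AEs, and a liver finding that meets the alert criteria is an AE of special interest and is listed separately. None of this gives a dose-group summary at Day 176.

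**AEs starting after Day 113.** A reader might also infer that the drug-related AE endpoint, which SAP 5.2.2 illustrates as a number of subjects, is undercounted. The REP cut is the protocol's treatment-emergent rule, and the SAP's wording is only an example. The period after the cut is 63/175 = 36% of post-dose days, so it would hold 36% of onsets at a constant background rate. If the rate instead tracked drug amount, the share would be (2^(−16/T) − 2^(−25/T)) / (1 − 2^(−25/T)), with T the half-life in weeks:
- T = 4 (Protocol 3.2): (0.0625 − 0.0131)/0.9869 = 5.0%.
- T = 3 (Protocol 1.2.4, ADA-negative patients): (0.0248 − 0.0031)/0.9969 = 2.2%.

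Both rate models are assumptions. With no placebo group, a longer AE window would probably add mostly background events, so no extra AE count is required.

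**Conclusion.** The point holds as a cheap improvement, with moderate confidence. On the most natural reading, one scheduled lab day of six and one vital-sign time point of 17 are outside the by-visit tables, and Day 176 ALT and bilirubin are outside the eDISH plot. Summarising them serves the end-of-trial assessment named in Protocol 7.3.4 and matches what the SAP already does for body weight.

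The conclusion rests on two assumptions: that the explicit phase statements in SAP 6.1 and 7.8.1 override the printed nesting of Follow-up under On treatment, and that Section 15.4 does not already contain a Day 176 summary. It concerns subjects examined after Day 113. Anyone who leaves earlier has the closing examination inside the on-treatment phase.

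The 16-week restriction is acceptable as the main analysis.

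**What to change.** Keep the 16-week on-treatment summaries as the main analysis, and:

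1. In SAP 6.1, state in one sentence that Follow-up is not part of On treatment.
2. In SAP 7.8.2 and 7.8.3, add a Day 176 (EoTrial) row, labelled follow-up, with change from baseline for labs, blood pressure, pulse rate and respiratory rate. Body temperature stays listed only, as planned.
3. In SAP 7.8.2, show Day 176 ALT and total bilirubin in the eDISH plot, marked as follow-up.

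A dosing-to-EoTrial AE summary is optional, since Protocol 7.3.4 allows further analysis intervals to be defined in the SAP. If added, it should be labelled supportive.

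The cost is a few table rows, one plot marker and short SAP wording. All the data are already collected and no protocol rule changes.
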